## **7.1 Study-Stop Criteria**

The entire study or a single dosing arm may be discontinued or not initiated at the discretion of the Sponsor based on the occurrence of the following:

- AEs with respect to their nature, frequency, severity, and/or duration
- Medical or ethical reasons affecting the continued performance of the study
- Difficulties in the recruitment of patients
- Cancellation of drug development

The entire study will be discontinued by the sponsor if there are three or more related Grade 3 or Grade 4 treatment-emergent adverse events (TEAEs) of the same Common Terminology Criteria for Adverse Events (CTCAE) category.

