The PI will rate the severity of AEs using the CTCAE v4.03 to grade the severity. Each CTCAE v4.03 term is a Medical Dictionary for Regulatory Activities (MedDRA) Lowest Level Term (LLT). The CTCAE displays Grades 1 through 5 with unique clinical descriptions of severity for each AE. Not all Grades are appropriate for all AEs. Therefore, some AEs are listed with fewer than five options for Grade selection. Grade 5 (Death) is not appropriate for some AEs and, therefore, is not an option.

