## 11.2 Criteria for Determining Relationship to Drug

The PI will make a blinded determination of the relationship of the AE to NGM282 (including placebo) in the double-blind cohort. An open-label determination of the relationship of the AE to NGM282 and a separate open-label determination of the relationship of the AE to rosuvastatin will be made in the open-label single-blind cohort. The PI will make a blinded determination of the relationship of the AE to NGM282 (including placebo) and a separate open-label determination of the relationship of the AE to rosuvastatin in the placebo-controlled 24-week histology cohort. All determinations of relationship will be made using a four-category system (not related, possible, probable, or definite) according to the following guidelines:

- **NOT RELATED** = an AE that does not follow a reasonable temporal sequence from administration of the drug and that can be reasonably explained by other factors, including underlying disease, complications, concomitant drugs, or concurrent treatment;
- **POSSIBLE** = an AE that follows a reasonable temporal sequence from the administration of the drug (including the course after withdrawal of the drug) and that cannot be excluded as being possibly caused by the drug (e.g., existence of similar reports attributed to the drug and/or its analogues; reactions attributable to the pharmacological effect of the drug), although other factors such as underlying disease, complications, concomitant drugs, or concurrent treatment are presumable;
- **PROBABLE** = an AE that follows a reasonable temporal sequence from administration of the drug (including the course after withdrawal of the drug) and that can be excluded as being possibly caused by other factors, such as underlying disease, complications, concomitant drugs, or concurrent treatment.
- **DEFINITE** = an AE that follows a reasonable temporal sequence from administration of the drug (including the course after withdrawal of the drug), follows a known or hypothesized cause–effect relationship, and (if appropriate) satisfies the following:
  - Positive results obtained in drug sensitivity tests
  - Toxic level of the drug present in blood or other body fluids

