## 11.3 Reporting

An SAE is any untoward medical occurrence at any dose that results in any of the following outcomes:

- Death
- A life-threatening event (i.e., places the subject, in the view of the PI, at immediate risk of death)
- Inpatient hospitalization or prolongation of existing hospitalization

- A persistent or significant incapacity or substantial disruption of the ability to conduct normal life functions
- A congenital anomaly/birth defect
- Important medical events that may not result in death, be life-threatening, or require hospitalization may be considered SAEs when, based upon appropriate medical judgment, they may jeopardize the subject and may require medical or surgical intervention to prevent one of the outcomes listed in this definition.

An unexpected adverse drug event is any adverse drug event the specificity or severity of which is not consistent with the current IB or, if an IB is not required or available, the specificity or severity of which is not consistent with the risk information described in the general investigational plan or elsewhere in the current application.

An AE is associated with the use of the drug if a reasonable possibility exists that the event may have been caused by the drug.

SAEs that are unexpected and related to either NGM282 or rosuvastatin are reportable to Regulatory Authorities. All SAEs will be reported by the PI to the Sponsor and will be reported to the responsible Ethics Committee (EC) in accordance with local requirements.

The Sponsor's assigned Safety Representative will be notified in writing (e.g., email or facsimile) within 24 hours of when an SAE is first recognized or reported. The Safety Representative will subsequently notify the Sponsor and the Sponsor's assigned Medical Monitor of all reported SAEs.

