#### **11.4           Cardiovascular Adjudication**

An external independent Cardiovascular Adjudication Committee (CAC) will adjudicate serious adverse events (SAEs). The CAC members will be independent of the Sponsor, the clinical study sites and Investigators. The blinded medical review of known or suspected Major Adverse Cardiovascular Event (MACE) will primarily focus on CV death, myocardial infarction, cerebrovascular accident (stroke), and hospitalization for heart failure. Sites may be asked to provide additional source documentation relevant to any event reported to the CAC as they would to study safety personnel for any serious safety event. Further details are retained in the CAC Charter for the NGM282 Program.

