### **12.10.1 Adverse Events**

AEs, including serious AEs, will be coded using the MedDRA. The number and percentage of subjects experiencing an AE will be summarized for each system organ class (SOC) and preferred term (PT) by treatment group. In addition, AEs will be tabulated according to intensity, causality, and relation to the study drug. Individual data listings for AEs will be presented for each subject.

All AE summaries will be restricted to TEAEs only. TEAEs are defined as AEs that commence on or after the time of start of first study-drug administration. AEs without an onset date or time will be defined as treatment emergent, except if an incomplete date (e.g., month and year) clearly indicates that the event started prior to the start of first administration of study drug or if the AE stop date indicates that the event started or stopped prior to the start of first administration of study drug.

For the summaries of AEs, subjects who experience the same AE (in terms of the MedDRA preferred term) more than once will be counted only once for that event. Separate summaries will be provided for AEs by intensity, causality, and relationship to study drug.

All AEs will be listed. SAEs will be summarized and listed.

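### The only mandatory study-stop rule (Protocol 7.1) counts related Grade 3 and 4 events but, read literally, leaves out related deaths (Grade 5)

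*Protocol*

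**What the plan says.** Section 7.1 of the protocol has two parts. The first is discretionary: the study or a dosing arm "may be discontinued or not initiated at the discretion of the Sponsor based on the occurrence of the following". The listed grounds are the pattern of adverse events, medical or ethical reasons, recruitment difficulty, and cancellation of development. The second is a single mandatory sentence, under which the sponsor must discontinue the whole study if "there are three or more related Grade 3 or Grade 4 treatment-emergent adverse events (TEAEs" of the same CTCAE category.

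Section 11.1 adopts CTCAE v4.03: "The CTCAE displays Grades 1 through 5 with unique clinical descriptions of severity for each AE". It identifies the top grade as death: "Grade 5 (Death) is not appropriate for some AEs and, therefore, is not an option".

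The other places that deal with serious or fatal events are:

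- **11.3:** "All SAEs will be reported by the PI to the Sponsor". The section sets reporting duties and no stopping rule.
- **11.4:** an independent committee adjudicates events. "The blinded medical review of known or suspected Major Adverse Cardiovascular Event (MACE) will primarily focus on CV death", among other events. No stopping rule is given.
- **8.2:** treatment of an individual subject ends on any TEAE of Grade 4 and above. This does not act on the study as a whole.
- **12.12:** the interim analysis of the 24-week cohort reviews safety, but the study will not be stopped early on its results.
- **SAP 9.2:** one planned table covers TEAEs of Grade 3 and above.

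**The concern.** An automatic stopping rule exists to take the decision out of the sponsor's hands once a stated level of harm is reached. It should therefore never give a weaker response when one of the counted events turns out worse. The rule in 7.1 does: if one of three related Grade 4 events is instead fatal, the count falls from three to two and the mandate to stop disappears.

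A death judged related to study drug is one of the outcomes such a rule is most needed for. The protocol foresees fatal events in this population. Section 5.1.1 cites mortality of 1% to 2% per year in NASH with fibrosis, largely cardiovascular. Section 5.5 says the clinical outcomes of long-term LDL-C elevation with NGM282 are unknown. Neither statement estimates the chance of a *related* death, but both show that the case is not fanciful.

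**Working it through.** The documents state no operating characteristic for the rule, so there is no figure to reproduce. The check is to apply the rule as written, and the same rule with Grade 5 included, to the same sets of events.

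**Inputs.** Threshold of three, relatedness, same-category condition and Grades 3 and 4: section 7.1. Grade 5 as a separate grade meaning death: section 11.1.

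**Notation.** Within one CTCAE category, let n3, n4 and n5 be the numbers of related TEAEs of Grade 3, 4 and 5.

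- Rule as written: stop if n3 + n4 ≥ 3.
- Rule with Grade 5 included: stop if n3 + n4 + n5 ≥ 3.

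| Related events in one category | (n3, n4, n5) | Count as written | Count with Grade 5 | Stop as written? | Stop with Grade 5? |
|---|---|---|---|---|---|
| Three Grade 3 | (3, 0, 0) | 3 | 3 | yes | yes |
| One Grade 3, two Grade 4 | (1, 2, 0) | 3 | 3 | yes | yes |
| Two Grade 4, one death | (0, 2, 1) | 2 | 3 | no | yes |
| One Grade 3, two deaths | (1, 0, 2) | 1 | 3 | no | yes |
| Three deaths | (0, 0, 3) | 0 | 3 | no | yes |
| Two deaths | (0, 0, 2) | 0 | 2 | no | no |
| One death | (0, 0, 1) | 0 | 1 | no | no |

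**Where the two rules differ.** They disagree only if all three conditions hold: n5 ≥ 1, n3 + n4 ≤ 2, and n3 + n4 + n5 ≥ 3.

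**Largest total without a mandated stop.** As written: 2 + n5, with no upper limit on n5. With Grade 5 included: 2. This describes the logic of the rule and is not a measure of risk.

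**Is the gap closed elsewhere?** No. Sections 11.3 and 11.4 ensure that deaths are reported and reviewed, 8.2 acts on one subject, and 12.12 rules out early stopping on its interim results. Section 8.2 and the SAP table are not competing study-level rules. They show only that open-ended grade wording is used elsewhere in these documents.

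**Why no probability is given.** The documents state no rate of related Grade 3 to 5 events and no share of them that is fatal. Section 5.1.3 reports no SAEs in the Phase 1 study or the type 2 diabetes study, so the case is expected to be rare. Nor is there a clean number of exposed subjects to use:

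- The trigger covers the entire study.
- In the 24-week cohort the investigator makes a "blinded determination of the relationship of the AE to NGM282 (including placebo) and a separate open-label determination" for rosuvastatin. The double-blind cohort is also judged blinded for NGM282, while the open-label cohort is judged open-label.
- Section 12.10.1 gives a start but no end for treatment emergence: "TEAEs are defined as AEs that commence on or after the time of start of first study-drug administration". AE recording itself runs through follow-up (11.1).

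**The case against.** The strongest reply is that nothing is lost in practice. If a related death occurred alongside other severe related events, the sponsor could stop the study or an arm at once under the discretionary part of 7.1. It would know promptly: section 11.3 requires the Safety Representative to be notified within 24 hours of an SAE being recognized, and that person then informs the sponsor and the Medical Monitor. Ethics committees receive SAEs under local requirements, and unexpected related SAEs go to regulators. What is missing is an automatic trigger, not authority or information, and no endpoint or estimate is affected. The wording is probably a drafting slip that many readers would correct silently, and a fatal event first recorded as Grade 3 or 4 might be counted anyway.

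A second reply is that the correction does not finish the job. Two related deaths in a category would still mandate nothing, while three related Grade 3 events would stop the study.

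Most of this stands as a limit on the size of the point. It does not remove the point. Discretion cannot repair a gap in the one sentence written to remove discretion, and a mandatory rule should not depend on readers supplying missing words. On the second reply, any rule with a threshold of three leaves smaller sets untriggered. Once Grade 5 is counted, the rule no longer gives a weaker result for a worse set of the same number of events, which is the fault identified here. Whether a single related death should by itself stop or pause the study is a separate decision that would need its own clause.

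**Conclusion.** The concern holds. Read literally, the only mandatory study-level stop excludes related fatal events, so a worse set of three related events in one category can fail to trigger a stop that a milder set of three would trigger.

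The size is limited to the automatic rule and to the combination of conditions set out above. The sponsor can already stop for any death at its discretion. The conclusion rests on a literal reading of the grades named in 7.1 and on the visible text containing no other mandatory stop for death. It does not depend on any assumed event rate. It should be fixed because the fault lies in the study's only automatic safety stop and is simple to correct.

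**What to change.** In section 7.1, change the grade condition of the mandatory sentence to *Grade 3 or higher*. Keep the threshold of three, the relatedness condition and the same-category condition. Every set of events that mandates a stop today still does.

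The cost is one phrase in a protocol amendment, with the written approvals from sponsor, investigator and ethics committee that section 13.1 requires for changes affecting patient safety. No extra data, staff or procedures are needed, because investigators already report all SAEs, including deaths, to the sponsor under 11.3.

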## **8 Enrollment Criteria**

### **8.1 Double-blind, Open-label Single-blind and Placebo-controlled 24 Week Histology Cohorts**

#### **8.1.1 Inclusion Criteria**

Patients who meet the following criteria may be included in the study:

1. Males and females between 18 and 75 years of age (except self-identified of Asian descent), able to comprehend and willing to sign an Informed Consent Form (ICF).
2. Histologically confirmed NASH diagnosis as defined by the NIH NASH Clinical Research Network (see [Appendix A, Kleiner 2005](#)) and liver biopsy criteria outlined below. A historical biopsy is acceptable if performed within the required time period and tissue slides are available for a qualified pathology read.

#### Double-Blind Cohort:

- a. NAS of at least 4 with 1 point in each component
- b. Histologic evidence of fibrosis without cirrhosis
  - i. Fibrosis stage 1-3
- c. Liver biopsy within 6 months of Screening.

#### Open-Label Single Blind Cohort:

- a. NAS of at least 4 with 1 point in each component
- b. Histologic evidence of fibrosis without cirrhosis
  - i. Fibrosis stage 1-3
- c. Liver biopsy within 12 months of Screening.
  - i. Dosing Groups 3 or 4 must have a liver biopsy within 3 months of Screening in order to serve as the baseline comparison for the additional EOT biopsy.

Placebo-Controlled 24 Week Histology Cohort:

- a. NAS of at least 4 with 1 point in each component
- b. Histologic evidence of fibrosis without cirrhosis
  - i. Fibrosis stage 2-3
- c. Liver biopsy within 3 months of Screening in order to serve as the baseline comparison for the additional EOT biopsy.

3. Total liver fat content of  $\geq 8\%$  as measured by MRI-PDFF (MRI may be used for up to 8 weeks from the date of the original scan, including use for re-screened subjects)
4. Insulin-resistant or stable T2D

Double-Blind Cohort:

- a. Stable T2D is defined as HbA1c  $\leq 8.5\%$  at Screening.
- b. Diabetes medications: require a stable regimen for at least 3 months prior to Day 1 and throughout the study.
- c. Insulin resistance will be based on fasting insulin level  $\geq 10\text{uIU/mL}$ .

Open-Label Single Blind:

- a. Stable T2D is defined as HbA1c  $\leq 9.5\%$  at Screening.
- b. Diabetes medications (except GLP1 agonists): require a stable regimen for at least 3 months prior to Day 1 and throughout the study.
- c. GLP1 agonists: require a stable regimen for at least 12 months prior to Day 1 and throughout study
- d. Insulin resistance will be based on fasting insulin level  $\geq 10\text{uIU/mL}$ .

Placebo-Controlled 24 Week Histology Cohort:

Patients with T2D or insulin resistance will be allowed to enroll under the following conditions listed below and patients who do not have T2D or insulin resistance can be enrolled as long as all other criteria are met.

- a. HbA1c  $\leq 9.0\%$  at Screening
- b. Patients taking diabetes medications (except GLP1 agonists) require a “stable” regimen for at least 3 months prior to Day 1 and throughout study.
  - i. GLP1 agonists and pioglitazone: require a stable regimen for at least 12 months prior to Day 1 and throughout the study.

- ii. Stable insulin dosing is defined as reasonable dosage adjustments to maintain glucose control.
5. Other therapies for NAFLD or NASH: requires a stable regimen for at least 3 months prior to the Screening biopsy of record and throughout the study. May include vitamin E, milk thistle, thiazolidinediones and pentoxifylline.

Double-Blind Cohort:

Includes statins.

Open-Label Single Blind and Placebo Controlled 24 Week Histology Cohorts:

Includes statins if the conditions below are met. Other therapies may include vitamin E ( $> 800$  IU Placebo cohort only), milk thistle, thiazolidinediones (open-label, single-blind only) or pentoxifylline.

- a. Patient can be defined as statin naïve or experienced at Screening based on the following definitions:
  - i. **Statin-naïve:** no administration of statins within 3 months prior to enrollment.
  - ii. **Statin experienced:** administration of  $\leq 50\%$  of the maximal dose of current statin therapy.
- b. Requires a stable regimen for at least 3 months prior to Screening through Week 2.

The following are the acceptable daily doses of approved statin therapies, including combination preparations of statins and other lipid lowering agents. Also listed under Concomitant Medications in [Section 9.7](#).

- Atorvastatin:  $\leq 40$  mg/d
- Fluvastatin:  $\leq 40$  mg/d
- Lovastatin:  $\leq 40$  mg/d (immediate release),  $\leq 30$  mg/d (extended release)
- Pitavastatin:  $\leq 2$  mg/d
- Pravastatin:  $\leq 40$  mg/d
- Rosuvastatin:  $< 20$  mg/d (Note: must be  $<$  not  $\leq$  20 mg/d)
- Simvastatin:  $\leq 40$  mg/d

6. The following liver enzyme parameters must be met at Screening:
  - a. ALT and AST  $\leq 250$  IU/L
  - b. Abnormal ALT defined as:  $\geq 30$  IU in males and  $\geq 19$  IU in females
  - d. AST  $\geq 30$  IU/L except for patients with a historical biopsy within 3 months of screening with NAS of at least 4 with 1 point in each component and fibrosis stage 2 or 3 (Placebo-Controlled Cohort only)
7. The following additional laboratory parameters must also be met at Screening:

- a. Total bilirubin must be within normal range. For patients diagnosed with Gibert's Syndrome, please contact medical monitor/designee
  - b. INR  $\leq$  1.3 (in the absence of warfarin or other anticoagulant therapy)
  - c. Creatinine clearance  $\geq$  90 mL/min as calculated by Cockcroft-Gault equation
  - d. Alpha fetoprotein (AFP)  $<$  100 ng/mL
  - e. LDL C  $\leq$  185 mg/dL (except Double-blind cohort and  $\leq$  165 mg/dL for the Open-Label Single Blind )
  - f. LDL-C must also be  $\geq$  50 mg/dL for **statin naïve** patients (Placebo cohort only)
  - g. Platelet count must be within normal limits 150-450 K/uL (Placebo- Controlled Cohort only)
8. Female patients must be of non-childbearing potential defined as women who have had a hysterectomy, bilateral oophorectomy, medically documented ovarian failure, or are documented postmenopausal (follicle stimulating hormone  $>$  40 mIU/mL).
9. Female patients of childbearing potential defined as including women  $<$  55 years of age with 2 years of amenorrhea (absence of menstruation) must have a negative serum pregnancy test at Screening and urine pregnancy test at the Day 1 visit prior to dosing.
10. Female patients of childbearing potential and male patients with a female partner of childbearing potential must agree to consistent and adequate birth control from Screening to 30 days after the last dose of study medication.

One of the following forms of contraception is required and male patients must also use a condom.

  - a. Hormone-containing contraceptive
  - b. Intrauterine device with a failure rate  $<$  1% per year
  - c. Cervical cap or diaphragm with spermicidal agent
  - d. Sterilization (tubal ligation or vasectomy)
11. Able and willing to comply with the dosing instructions for study-drug administration and able to complete the study schedule of assessments.

### 8.1.2 Exclusion Criteria

The following criteria will exclude patients from the study:

1. Clinically significant acute or chronic liver disease of an etiology other than NASH
2. Evidence of drug-induced steatohepatitis secondary to amiodarone, corticosteroids, estrogens, methotrexate, tetracycline, or other medications known to cause hepatic steatosis
3. History or presence of cirrhosis (compensated or decompensated) as determined by histology, relevant medical complications, and/or laboratory parameters

4. Prior liver transplantation
5. Any acute cardiovascular event (e.g. myocardial infarction, stroke, severe arrhythmia or hospitalization for any cardiac related event) or evidence of active cardiovascular disease within 6 months of Screening
6. History of bypass or bariatric surgery or planned procedure during the study period. Removal of a gastric balloon or lap band is permitted if surgery performed within 6 months prior to Day 1.
7. Type 1 diabetes
8. History of clinically significant unstable or untreated illness or any other major medical disorder that may interfere with patient treatment, assessment, or compliance with the protocol
9. Any contraindication or inability to obtain an MRI
10. Inability to obtain or any contraindication to liver biopsy (if a historical biopsy with viable tissue slides are not available within the required time period)
11. Screening ECG with clinically significant abnormalities as determined by the Investigator
12. Positive for HBsAg, anti-HIV, or anti-HCV plus HCV-RNA. Patients who are anti-HCV positive but HCV-RNA negative (secondary to treatment or viral clearance) are eligible as long as there is evidence of viral negativity for a minimum of 12 weeks.
13. History of malignancy diagnosed or treated within 2 years (recent localized treatment of squamous or non-invasive basal cell skin cancers is permitted; cervical carcinoma in situ is allowed if appropriately treated prior to Screening); patients under evaluation for malignancy are not eligible.
14. Clinically-relevant drug or alcohol abuse within 12 months of screening. A positive drug screen will exclude patients unless it can be explained by a prescribed medication; the diagnosis and prescription must be approved and documented as such by the Investigator.
15. Use of any prohibited concomitant medications as described in [Section 9.7](#) prior to Day1.
16. Prior participation in a clinical trial of NGM282

Double Blind Cohort:

Prior participation in a clinical trial of NGM282 is excluded.

Open Label Single Blind and Placebo Controlled 24 Week Histology Cohorts:

Prior participation in a clinical trial of NGM282 is excluded **unless** previously enrolled into a placebo arm of the trial.

17. Patient with severe allergic or anaphylactic reactions to recombinant therapeutic proteins, fusion proteins, or chimeric, human, or humanized antibodies.
18. Participation in a study of another investigational agent within 28 days or five half-lives of the drug (whichever is longer) prior to Screening

19. Any acute or chronic condition that, in the opinion of the Investigator, would limit the patient's ability to complete and/or participate in this clinical study.
20. Pregnancy or lactation
21. Use of ezetimibe, colesevelam, cholestyramine, niacin, PCSK9 inhibitors, or other lipid-lowering agents within 3 months of Screening (except Double-blind cohort).

Placebo-Controlled 24 Week Histology Cohort Only

Use of any other lipid lowering agents or combination preparation of statins **except** ezetimibe when approved by MM/designee as second line lipid management therapy, within 3 months of Screening and throughout study

- a. colesevelam, cholestyramine, niacin, PCSK9 inhibitors (evolocumab or alirocumab), colestid, fibrates, fenofibrates, pharmacologic/prescribed fish oil

22. History or presence of ALT elevations or significant side effects indicative of statin intolerance (except Double-blind cohort).
23. Use of weight loss medications including: orlistat, phentermine, topiramate, qsymia, lorcaserin hydrochloride, naltrexone hydrochloride, liraglutide (use is for weight loss not T2D, e.g. Saxenda®), benzphetamine, diethylpropion and phendimetrazine, within 3 months of screening and throughout study

Additionally for all cohorts, the Investigator has discretion to repeat assessments if he/she believes there is a good chance the results were spurious and do not accurately represent the patient's true values. Repeat assessments must be conducted within the Screening Period.

